10.2 ANALYSIS OF STAGE II (PHASE III STUDY)

Disease-free survival and overall survival curves will be estimated using the Kaplan-Meier method. The primary comparison of survival distributions will be with the logrank test. Secondary analyses will adjust for prognostic factors using appropriate regression models (e.g. Cox proportional hazards model). All measures of efficacy will be compared by an intention-to-treat analysis including all randomized patients. Toxicity will be analyzed by treatment received. Ninety-five percent confidence intervals will be reported for the differences between the treatment arms.

Descriptive statistics for treatment-related adverse events as well as Quality of life (FACT-Cx, SF-12, MDASI, EQ-5D) and subscales (physical well-being, social well-being, emotional well-being, functional well-being, cervical cancer specific well-being and body image scale), will be calculated for each randomization group at each assessment.

Similarly, descriptive statistics will also be calculated for other outcomes, such as pain scores, anxiety and depression scores and analgesic consumption, etc.

Continuous variables will be assessed for normality and equality of variances between groups. Discrete variables (eg. presence/absence of post-operative infection) will be summarized by frequencies/proportions.

For continuous variables, analysis of variance and/or regression will be used, where appropriate. If assumptions for these tests are violated, alternative non-parametric tests will be used. Difference between groups with respect to discrete variables will be evaluated by using chi-squared tests.

Exploratory analyses adjusting for prognostic factors including age, tumor size, stage, grade of differentiation, depth of myometrial invasion, lymph node involvement, type of treatment, and ECOG status will be performed using proportional hazards regression methods. The impact of baseline QoL on survival will also be investigated.

Provided sufficient patient numbers, outcomes in regards to treatment costs will be analyzed country-specific by the individual investigator of that country.

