17.0 ADVERSE EVENTS (AEs)

17.1 DEFINITIONS

The Investigator is responsible for reporting all AEs that are observed or reported during the study, regardless of their relationship to treatment or their clinical significance.

An AE is defined as any untoward medical occurrence in a patient enrolled into this study regardless of its causal relationship to study treatment.

A treatment-emergent AE is defined as any event not present prior to surgery or any event already present that worsens in either intensity or frequency following surgery.

All AEs that occur after surgery during the study must be reported in detail in the patient's source/chart and the relevant electronic case report forms and followed to a satisfactory resolution or until the local Investigator deems the event to be chronic or the patient to be stable. The description of the AE will include the onset date, duration, date of resolution, severity, seriousness, etiology, and the likelihood of relationship of the AE to study treatment.

Severity of adverse events will be graded using the National Cancer Institute Common Terminology Criteria for Adverse Events version 3.0 (CTC-AE v3.0),

If an adverse event occurs which is not contained in the CTC-AE v3.0, the five-point scale below will be used:

- 1. Mild: discomfort noticed but no disruption of normal daily activity.
- 2. Moderate: discomfort sufficient to reduce or affect daily activity.
- 3. Severe: inability to work or perform normal daily activity
- 4. Life Threatening: represents an immediate threat to life
- 5. Death

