17.7 ASSESSMENT OF CAUSALITY

The Investigator's assessment of an AE's relationship to treatment is part of the documentation process, but it is not a factor in determining what is or is not reported in the study. If there is any doubt as to whether a clinical observation is an AE, the event should be reported.

The relationship or association of the test article in causing or contributing to the AE will be characterized using the following classification and criteria:

Version 4 October 2014

- Unrelated: This relationship suggests that there is no association between the surgery and the reported event.
- Possible: This relationship suggests that treatment caused or contributed to the AE, i.e. the
 event follows a reasonable temporal sequence from the time of surgery and/or follows a
 known response pattern to the surgery, but could also have been produced by other factors.
- Probable: This relationship suggests that a reasonable temporal sequence of the event with
 drug administration exists and the likely association of the event with the surgery. This will be
 based upon the known or previously reported complications to the surgery, or judgment based
 on the Investigator's clinical experience.
- Definite: This relationship suggests that a definite causal relationship exists between the surgery and the AE, and other conditions (concurrent illness, progression/expression of disease state, or concurrent medication reaction) do not appear to explain the event.

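### Section 10.2 names only treatment-related adverse events for the summary by randomisation group, and no all-cause adverse event comparison by randomised arm is stated

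*Protocol*

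**What the plan says.** Section 10.2 names the adverse event summary: "Descriptive statistics for treatment-related adverse events as well as Quality of life" and its subscales, for each randomisation group at each assessment.

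The same section makes two other statements that bear on safety. One is "Toxicity will be analyzed by treatment received", followed by a promise of 95% confidence intervals for differences between arms. The other is general: "Discrete variables (eg. presence/absence of post-operative infection) will be summarized by frequencies/proportions", and "Difference between groups with respect to discrete variables will be evaluated by using chi-squared tests". Neither mentions relatedness.

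Section 17 collects more widely than the summary uses. Section 17.1 has the investigator report all events "regardless of their relationship to treatment or their clinical significance", and it defines a further set: "A treatment-emergent AE is defined as any event not present prior to surgery or any event already present that worsens" after surgery. Section 10 never uses that set. Section 17.5 runs collection from consent to 6 months after treatment, with relationship to treatment specified by the investigator. Section 17.7 says of the causality assessment that "it is not a factor in determining what is or is not reported in the study". Section 5.0 describes the trial as open-label.

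**The concern.** In a randomised trial, the comparison of all events by allocated arm is protected by randomisation whatever anyone believes about cause. A comparison limited to events judged related loses that protection if the judgement depends on the arm. Here the person judging knows the arm, and section 17.7 tells them to weigh the known response pattern to the surgery, which may differ between open and minimally invasive operations. A difference could then appear where there is none, or a real one could be masked.

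This matters because treatment-associated morbidity within 6 months is a stated secondary objective (section 1.0), and section 10.4 records a concern about severe adverse events in the minimally invasive arm. Section 10.2 also leaves open which section 17.7 grades (possible, probable, definite) count as treatment-related.

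**Working it through.** The point is textual, and the plan has no figure of its own to reproduce.

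**Step 1: what each stated safety analysis covers.**

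| Statement | Events covered | Grouping |
|---|---|---|
| 10.2, adverse event summary | treatment-related | randomisation group |
| 10.2, toxicity | no relatedness filter stated | treatment received |
| 10.2, discrete variables | individual outcomes such as post-operative infection, no filter stated | groups, chi-squared test |
| 7.2, morbidity | complications listed by name, under a heading that calls the morbidity treatment-related | not stated there |
| 10.4 and 19.1, safety committee | all toxicity data; grade 3 and 4 events, serious events, deaths | monitoring |

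No row states both all events regardless of cause and the randomised groups. The toxicity row comes closest, but it regroups patients. Section 10.2 does not say how a patient converted to laparotomy is classed there.

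**Step 2: how far differential attribution could move the filtered summary.** The 370 per arm comes from section 9.0 (740/2). The event rates and attribution shares are assumptions; the documents give none.

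Let p be the true all-cause rate, the same in both arms, and let a and b be the shares called related in each arm. Then:

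- p1 = p × a and p2 = p × b
- SE = √[p1(1 − p1)/370 + p2(1 − p2)/370]
- z = (p1 − p2)/SE
- P(significant) = Φ(z − 1.96) + Φ(−z − 1.96)

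| p | a v b | p1 v p2 | False difference (points) | SE | z | P(significant) |
|---|---|---|---|---|---|---|
| 30% | 90% v 80% | 27.0% v 24.0% | 3.0 | 0.0320 | 0.94 | 0.155 |
| 30% | 90% v 75% | 27.0% v 22.5% | 4.5 | 0.0317 | 1.42 | 0.295 |
| 30% | 90% v 60% | 27.0% v 18.0% | 9.0 | 0.0305 | 2.95 | 0.839 |
| 20% | 90% v 75% | 18.0% v 15.0% | 3.0 | 0.0273 | 1.10 | 0.196 |
| 40% | 90% v 75% | 36.0% v 30.0% | 6.0 | 0.0345 | 1.74 | 0.413 |

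With equal attribution the last column would be 0.05.

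**Step 3: the reverse case.** Suppose the true rates are 40% and 30%. A comparison of all events has power of about 0.82 at 370 per arm. If 60% of events are called related in the first arm and 80% in the second, the filtered rates are 0.40 × 0.60 = 24% and 0.30 × 0.80 = 24%, and the difference disappears.

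**Step 4: limits of steps 2 and 3.** The quoted sentence promises descriptive statistics, not a test. The probabilities show how large the distortion could be. They are not the error rate of a planned analysis.

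**Step 5: whether the data for a wider summary exist.** Section 17.1 records severity and seriousness on each adverse event, and section 17.5 covers the period to 6 months. Serious event reports are narrower: section 17.4 asks for them to 30 days after primary therapy, and up to 6 months only when directly related to it. An all-cause comparison built on those reports alone would bring attribution back in after day 30.

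**The case against.** A reader might infer that the whole safety comparison turns on attribution. The documents do not support that. The toxicity analysis and the chi-squared comparisons carry no stated relatedness filter. Section 7.2 lists wound complications, ileus, urinary infection and retention, and nerve injury by name, and the safety committee sees all toxicity data.

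A reader might also infer that the operating surgeon grades causality. Section 6.8 accredits site principal investigators on surgical skill, which makes that likely in many cases. Sections 17.5 and 17.7 say only that the investigator does it.

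There is a gentler reading of the wording too. Section 7.2 uses almost the same phrase for its morbidity outcome, which is a list of complications in time windows. If section 10.2 means that list, no causality grade enters and the distortion in steps 2 and 3 does not arise. Section 10.2 does not say which meaning applies, and on this reading too it still states no all-cause comparison by randomised arm.

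Finally, the full set of adverse event tables commonly sits in a statistical analysis plan, which is not at hand, and nothing in 10.2 forbids an all-cause table. That limits the weight of the point. It does not remove it, because the protocol does name a set of events, and it is the narrower one.

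**Conclusion.** The point holds in a limited form. The one adverse event summary that section 10.2 assigns to the randomised groups is of treatment-related events. The other general toxicity analysis is by treatment received. No all-cause comparison by randomised arm is stated, although the events are collected and a treatment-emergent definition stands ready in section 17.1.

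If relatedness means the investigator's causality grade, that summary is open to differential attribution. Under the assumed inputs, the false difference is 3 to 9 points at a true rate of 30%. No document figure shows that attribution would differ between arms, so this is a vulnerability and not a demonstrated bias. It does not extend to the named complications, the chi-squared comparisons or the safety committee's monitoring. It merits a short amendment and does not undermine the trial's safety evidence as a whole.

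**What to change.** In section 10.2:

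- Summarise all treatment-emergent adverse events, as any event and as grade 3 or higher, by randomised arm to 6 months from surgery, whatever the causality grade.
- Keep treatment-related events as a supportive table, and state which section 17.7 grades (possible, probable, definite) are included.
- For serious events, either use the seriousness item on the adverse event record, or limit the all-cause comparison to 30 days, because section 17.4 requires later reports only when they are directly related to primary therapy.
- State how this summary sits beside the toxicity analysis by treatment received, including how converted patients are classed in the latter.

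The cost is a few sentences and one extra table, from data already collected. Unrelated events will dilute the comparison somewhat. They should fall on both arms alike, so the loss is in precision and not in validity.

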2.4 LAPAROSCOPY FOR SURGICAL TREATMENT

Laparoscopic radical hysterectomy was described initially by Canis et al.⁵⁰ and Nezhat et al.⁵¹. Since those initial reports, a number of other groups have published their experiences showing the feasibility and safety of this procedure⁵² ⁵³ ⁵⁴ ⁵⁵ ⁵⁶ ⁵⁷. These reports suggest performing the procedure laparoscopically in no way adversely affects the patient's overall prognosis and survival⁵⁸ ⁵⁹ ⁶⁰ ⁶¹ ⁶² ⁶³. Nevertheless, few long-term data are available on the morbidity of laparoscopic radical hysterectomy and survival after this procedure.

To date, no randomized trials have been completed which directly compare laparoscopic and open radical hysterectomy. The largest series thus far on laparoscopic radical hysterectomy, by Spirtos et al⁶⁴, describes 78 consecutive patients, all with early cervical cancer. In that series, 94% of the procedures were completed laparoscopically. The average operative time was 205 min, and the average blood loss was 225 mL. One patient (1.3%) required a blood transfusion, 3 patients had unintended cystotomies, 2 patients required laparotomy to control bleeding, and 1 patient suffered an ureterovaginal fistula. Three patients had microscopically positive or close margins. The authors reported a recurrence rate of 5%.

Obermair et al.⁶⁵ reported upon the feasibility and safety of total laparoscopic radical hysterectomy (TLRH) in 55 patients with cervical (39), endometrial (8), vaginal (2), or recurrent colon cancer (1), or severe pelvic endometriosis (5) followed for 3 years. The median total operating time was 210 minutes, and median hospital stay was 5 days. Intraoperative complications included three vascular injuries and one obturator nerve palsy, all of which occurred in the first half of the series. Early postoperative morbidity included deep vein thrombosis, pulmonary embolism, bladder infection and dysfunction, and vaginal fistula. These events occurred less frequently in the second half of the series. Late

Version 4 October 2014 LACC Trial Page 17 of 105 postoperative morbidity consisted of lymphedema, pelvic abscess and lymphocyst formation, pelvic cellulitis, hyperesthesia of the leg, and small bowel obstruction. It was concluded that TLRH carries acceptably low morbidity that can be reduced with experience with the technique.

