7.2 SECONDARY OUTCOME MEASURES

Patterns of recurrence: date and localization of 1st recurrence as confirmed histologically –
 pelvic versus distal.

- Treatment related morbidity, as evaluated by:
 - Intraoperative complications injury to bladder, ureter, bowel; vascular injury and bleeding, nerve injury;
 - Perioperative (time to discharge from hospital): urinary tract infection, urinary retention, ileus, cardiac (myocardial infarction, atrial fibrillation), pulmonary (edema, atelectasis, pneumonia), renal and cerebrovascular morbidity. Wound and vault complications (infection, breakdown, and dehiscence). Septicaemia and thromboembolic complications (DVT, PE). Lymphocyst or abscess formation;
 - Early postoperative (< 4 weeks): Wound and vault complications (infection, dehiscence). Lymphocyst, Abscess formation, Lymphoedema or Fistula formation;
 - Long-term morbidity (4 weeks to 6 months): Lymphoedema, incisional hernia formation, vaginal eviseration.
 - Estimated blood loss: As defined by the total volume of suctioned fluids minus the volumes of irrigation fluids used at the completion of surgery. In addition, blood loss will be reviewed in hemoglobin change from baseline. A Full Blood Count (hemoglobin) will be taken before and the morning after the operation;
 - Postoperative pain and analgesic consumption using pain scores and analgesic consumption measurements;
- Costs: measured as the incremental cost per unit of improvement in functional outcome, measured in terms of the primary outcome plus using quality-adjusted life years (QALYs) to undertake a cost-utility analysis;
- Quality of life: Change in Quality of Life using Functional Assessment of Cancer Therapy Cervical (FACT-Cx), the MD Anderson Symptom Inventory (MDASI, Short Form-12 (SF-12) and EuroQoL-5D (EQ-5D) between Baseline (pre-surgery) and 6 months after surgery.
- Pelvic Floor Distress Inventory: measures symptom severity and quality of life changes in women with pelvic floor disorders. The Pelvic Floor Distress Inventory (PFDI) provides a standardized, reproducible assessment of the patient's symptoms and their effect on daily life⁸⁸.
- Overall survival at 4.5 years follow-up
- Feasibility of sentinel lymph node biopsy in this group of patients.

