11.1 ECONOMIC ANALYSIS

We will assess the cost-effectiveness of the intervention (TLRH \pm Laparoscopic Pelvic/Aortic Lymph Node Dissection) relative to standard treatment alone (TARH \pm Pelvic/Aortic Lymph Node Dissection), calculated as the incremental cost per unit of improvement in functional outcome, and measured in terms of the primary outcome.

The outcomes of this part of the economic analysis will be in terms of costs per disease and treatment specific difference in quality of life at six months. More specifically, costs per fewer days' treatment-related morbidity, shorter hospital stays, less days with post-operative pain, and less analgesic consumption. By assessing the difference in cost between the standard treatment and the proposed intervention, it can be ascertained which of the two treatments represents the most sound investment in terms of the improvement in quality of life.

We will also measure the quality-adjusted life years (QALYs) gained with the intervention and use this to undertake a cost-utility analysis. The QALY calculations will be based on health status measures for trial participants, with valuations of changes in health status and quality of life based on the EQ-5D. Several viewpoints will be considered for the economic analyses, including those of health system purchasers, households and society in general.

This part of the economic analysis allows us to express outcomes in costs per QALY. The aim of this generic outcome measure is to assess whether the study intervention represents value for money as compared to alternative interventions (including for other conditions), and as compared to the various threshold values below which an intervention is considered good value for money (in Australia \$40,000 per QALY is often used).

In terms of measuring costs, a number of components will be considered, including: the intervention costs; the provision of information booklets to patients; GP and specialist consultations; radiology and imaging; prescriptions, over-the-counter medications; community health and social services; days off work; and informal care by family and friends. Direct costs will be obtained for samples of patients, stratified by hospital, operation and outcome, using a bottom-up approach by recording the volume of resource use in both arms of the trial, and then applying a unit cost to each component. Data on all patients' use of healthcare services will be collected using a combination of retrospective

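### Section 10.2 lets an assumption check choose the test, and so the quantity compared, for continuous secondary outcomes; the unnamed fallback, if a rank test, does not remedy unequal variances

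*Protocol*

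**What the plan says.** The rule is in protocol section 10.2 and has three steps.

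- Check: "Continuous variables will be assessed for normality and equality of variances between groups".
- Default: "For continuous variables, analysis of variance and/or regression will be used, where appropriate".
- Fallback: "If assumptions for these tests are violated, alternative non-parametric tests will be used".

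No check, threshold or replacement test is named. An earlier paragraph of the same section states: "Ninety-five percent confidence intervals will be reported for the differences between the treatment arms". It does not say differences in what.

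The rule reaches the continuous secondary outcomes of section 7.2: estimated blood loss, pain scores, analgesic consumption, the pelvic-floor inventory, and quality of life ("Change in Quality of Life using Functional Assessment of Cancer Therapy" and the other instruments, from baseline to 6 months). It does not reach the primary endpoint: "The primary comparison of survival distributions will be with the logrank test".

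**The concern.** ANOVA and regression compare means. The usual non-parametric replacement, the rank-sum test, asks whether a value from one arm tends to exceed a value from the other. These are different quantities, so under section 10.2 the result of an assumption check settles which one is tested.

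Two features make this a poor rule and not merely an undetailed one.

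- Unequal variance is an explicit trigger, but a rank test does not remedy it. Welch or heteroscedasticity-robust standard errors do.
- With several hundred women per arm, regression tolerates non-normality well, while a formal normality test would reject for almost any skewed or bounded score. The switch would then be routine where it is least needed.

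At stake is the coherence of the secondary results. A p-value could favour one arm while the mean difference beside it is nil, or be non-significant while the interval for the mean difference excludes zero. The analyst also keeps a choice of test in an open-label trial.

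**Working it through.** **Inputs.** The protocol gives no standard deviation, distribution or power figure for any continuous outcome, so there is no stated figure to reproduce. From the documents: 370 per arm (section 9.0), used only as an upper limit for n; 50 per arm (Stage 1); and, for the share of women who might form a heavy tail, the 78-patient laparoscopic series in section 2.4 ("In that series, 94% of the procedures were completed laparoscopically", so 6% were not). Everything else below is assumed. Tests are two-sided at 5%.

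**Check 1: skewed arms, equal means, different spread (assumed lognormal).** The mean is exp(μ + σ²/2). With log-SD 0.6 and 0.8, equal means require a difference in μ of (0.64 − 0.36)/2 = 0.14, so the wider arm has a median exp(−0.14) = 0.87 times the other.

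- Probability that a value from the wider arm exceeds one from the other: Φ(−0.14/√(0.36 + 0.64)) = Φ(−0.14) = 0.444, which is 0.056 below one half.
- Null standard error of that proportion: √[(2n + 1)/(12n²)]. At n = 370 this is √(741/1,642,800) = 0.0212.
- Expected z = 0.0557/0.0212 = 2.62, so the rejection probability is about Φ(2.62 − 1.96) = 0.75.
- At n = 50 the standard error is √(101/30,000) = 0.0580, z = 0.96, and rejection is about 16%.

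Simulation agrees: rank-sum 74.4% and 15.9%, Welch 4.7% and 5.3%. The whole two-stage rule (assumed: Shapiro-Wilk in each arm plus Levene at 0.05, then rank-sum or pooled t) gave 74.7% and 16.2%, and the check failed in every run.

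**Check 2: one arm contaminated, equal means.** Assumed: open arm gamma with mean 100 and CV 0.4; in the minimally invasive arm a fraction p averages r times the open mean, and the rest average (100 − 100pr)/(1 − p). For p = 6%, r = 2 the rest average 88/0.94 = 93.6. Simulated rejection at 370 per arm (ranges are over repeated runs):

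| p | r | mean of the rest | rank-sum | Welch |
|---|---|---|---|---|
| 6% | 1.5 | 96.8 | 6–7% | about 5% |
| 2.6% (2/78) | 2 | 97.4 | 6–7% | about 5% |
| 6% | 2 | 93.6 | 14–16% | about 5% |
| 10% | 2 | 88.9 | 36–38% | about 5% |
| 6% | 2.5 | 90.4 | 43–46% | about 5% |

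At 100 per arm the last three rows fall to roughly 8–15%, and at 50 per arm to roughly 7–10%.

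**Check 3: a real mean difference missed.** With 10% at 2.5 times and the rest at 0.92 times, the mean is 25 + 82.8 = 107.8, or 7.8% higher. Welch power is 48–49%, rank-sum 6–7%. For lognormal arms with equal medians and log-SD 0.6 and 0.8, the mean ratio is exp(0.14) = 1.15: Welch 64%, rank-sum 5%.

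**Check 4: cases where the rank test does well.**

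- Identical lognormal arms: both tests about 5%.
- Symmetric data with SDs 1 and 2: rank-sum 6.0% at 370 per arm, so the inflation needs skew.
- Lognormal arms of equal shape shifted by 0.2 SD, 370 per arm: rank-sum power 99%, Welch 77%.
- A true 3.4% lower mean (6% at 2 times, the rest at 0.90 times: 12 + 84.6 = 96.6): rank-sum 59%, Welch 19%.
- Very different spread (log-SD 0.5 and 1.0, equal means): Welch itself drifts to 6.0% at 370 per arm and 7.4% at 50.

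**The case against.** The strongest reply is that the sentence is generic and much has been read into it.

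- **No mean difference is promised.** A reader might infer that the confidence intervals in section 10.2 are for mean differences, so that a rank test breaks a commitment. The text says only differences between arms, in a paragraph on survival, efficacy and toxicity. The mean target is inferred from ANOVA and regression. This stands.
- **No rank test and no formal pre-test is named.** A permutation test or a bootstrap of means is also non-parametric, and a statistician could judge ANOVA adequate at this size. This stands too, so every figure above is conditional on the usual choice. But an open fallback behind an open trigger is itself the weakness, and nothing in the protocol steers towards a test that still targets means.
- **The contamination ratios are not in the documents.** No blood-loss or pain figures are given for converted women. The series behind the 6% reports only 2 of 78 needing laparotomy for bleeding, and another cited series had no conversions. Mild assumptions give near-nominal error. This stands and sets the lower end of the range.
- **The rank test detects a real difference in distribution.** In Check 2 most women in the contaminated arm do better, and for pain or blood loss the typical patient may be the better target. That is a legitimate choice of effect measure, but it should be made in advance, not by an assumption check.
- **The details belong in the SAP.** Naming the tests does. The complaint is that the protocol fixes a switching rule.

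**Conclusion.** The concern holds in limited form. Section 10.2 makes the test, and with a rank-based fallback the quantity compared, depend on an unspecified check, and it answers unequal variances with a method that does not address them. Under assumed skewed arms of different shape and equal means, rank-sum rejection at 370 per arm runs from 6–7% to 14–46%, and to about 74% in one lognormal case, against about 5% for Welch. It is much smaller at 50–100 per arm under the contamination scenarios. None of these is an estimate for this trial: they rest on assumed distributions, a rank-sum fallback and a formal pre-test.

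Two stronger readings are not supported. The first is that rank tests are wrong here in general: with equal shapes or a pure shift they are valid and can be more powerful. The second is that the switch corrupts the economic results. Section 11 is a separate, optional and country-specific analysis with its own measure ("calculated as the incremental cost per unit of improvement in functional outcome"), and nothing says the section 10.2 fallback governs it.

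The primary logrank comparison, the 740 patients and the equivalence margin do not change. This is a secondary-outcome matter, worth correcting because the correction is cheap.

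**What to change.** In section 10.2, delete the assumption-triggered switch and state one prespecified analysis for each continuous outcome:

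- regression on randomised arm, with the baseline value as covariate where collected (the quality-of-life instruments and the pelvic-floor inventory are; Appendix 1 schedules the pain scale only after surgery);
- heteroscedasticity-robust standard errors, or Welch where there is no covariate;
- the between-arm mean difference with its 95% CI as the reported effect;
- medians, quartiles and a rank test as a labelled sensitivity analysis that does not replace the main result.

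Add a sentence to section 11.1 that cost and QALY differences are compared as means with bootstrap confidence intervals, so that no one later applies the section 10.2 wording to them.

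The cost is one paragraph and one sentence, with no new data and no change to sample size. The downside is greater sensitivity to a few extreme values and some loss of power for heavily skewed outcomes under a pure shift (77% against 99% in Check 4). If the team prefers a typical-patient comparison for a particular outcome such as blood loss, it should name that effect measure and a matching interval in advance.
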